9. ASSESSMENTS AND PROCEDURES

9.1. Urine Sample Analysis

Urine samples (at least 8 mL) will be collected from a clean-catch mid-stream urine specimen at V1 and V3. Patients will be instructed to follow the clean catch instructions provided at the collection site. The Investigator or delegate may collect the urine samples using a properly disinfected collection techniques such as through a newly-placed urinary catheter, cystoscopy, or suprapubic aspiration, as per clinical indication (See Appendix II for further procedural guidance). Additional urine sample collection and analysis may be conducted at an unscheduled visit, if deemed necessary by treating Investigator. Specimens must be immediately refrigerated upon collection and submitted to the central laboratory within 24 hours of collection. Specimen must be stored and maintained at 2-8 °C when transporting. If transportation to the central laboratory is expected to exceed 24 hours, whole cups of urine specimen must be frozen.

Obtained urine samples will be labelled with subject ID, DOB, visit number, study ID, method of collection, date and time of collection. The collected sample will be placed in a small bag along with the test requisition form. The processing laboratory will aliquot the sample upon receipt, one to be analyzed by PCR (maximum 3mL) and the other to be analyzed by C&S (minimum 5mL). The sample will be stored under the appropriate temperature conditions until analysis of the sample.

Urine C&S

All urine samples for Urine C&S will be shipped to the central laboratory. Urine culture, isolation of uropathogen(s), initial identification of pathogen(s) and bacterial counts in urine will be conducted in the central laboratory.

Urine samples will be cultured and quantified using a calibrated loop to identify a quantitative count of bacteria at a lower limit of 10⁵ CFU/mL. All purified pathogen(s) will be further analyzed for species identification and antimicrobial susceptibility. The analysis results will be recorded in the source document and eCRF.

Urine PCR

Urine samples will be analyzed using the listed molecular testing devices:

• KingFisher Duo Prime

UPH-STD-05-01 Version: 0

Effective Date: 06/23/2023 Page 23 of 44

Doc Lab Inc. / Protocol Number 22-UPHUV-01 Advarra IRB Approved Version 0, Date: 12 May 2023 / Pro00071764

- QuantStudio 6 and 7 Flex Real-Time PCR System
- QuantStudio 12k Flex Real-Time PCR System

Bacterial and fungal pathogen-directed qualitative PCR amplification of target region of 24 uropathogens, and 16 different classes of resistance genes (see Appendix III. Device specification: pathogen targets and Cq ranges, antibiotics resistance genes and Cq ranges).

Further details of the standardized SOP for PCR procedure will be distributed from a central laboratory to all laboratory sites prior to the commencement of the study.

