UTI treatment and management affects healthcare costs and consumes vast resources in both ambulatory and inpatient settings. Outpatient management for UTIs is becoming limited due to the rising number of antimicrobial resistant cases. As a result of predisposing risks that alter normal urinary tract (functionally or anatomically), cUTI is associated with increased risk of recurrent infection. Furthermore, the management of cUTI starts with the use of empiric broadspectrum antimicrobial therapy that sufficiently covers the most commonly isolated uropathogens. In clinical practice, the choice of antibiotics is determined based on urine culture and antimicrobial sensitivity results. However, urine culture and sensitivity is a time-consuming procedure, where the turnaround time of the results is at least 48 hours, and this delay in a definitive diagnosis of cUTI and identification of infecting microorganisms often results in longer use of empiric broad-spectrum antimicrobial agents. An increased antimicrobial resistance in uropathogens underlying cUTI is attributed to an increased risk of recurrent infection, relapse, and exposure to multiple courses of antimicrobials, which can further complicate treatment course, prolong hospital stays, and lead to high mortality rates. The use of molecular testing for the diagnosis of UTI/cUTI, such as polymerase chain reaction (PCR), can facilitate the detection

UPH-STD-05-01 Version: 0

Effective Date: 06/23/2023 Page 13 of 44

of urinary pathogens with increased sensitivity and rapid turnaround times – that is typically less than 24 hours – and will enable the targeted administration of antimicrobial agents.

The proposed comparator PCR test has completed performance and clinical validation tests where it identified 15 bacterial genus and species, 4 fungal species, 5 STI-causing microorganisms, and 16 different classes of resistance genes. The study reported that all positive samples were identified via PCR at a rate of >90%, indicating that PCR may be more accurate, specific, and sensitive than culture. The clinical utilization of PCR-based diagnosis of UTI/cUTI would be extremely beneficial in ensuring timely treatment by rapid identification of infecting microorganisms and resistance, and eliminating empirical treatment by enabling early targeted treatment, ultimately reducing UTI-related morbidities and costs in a high-risk patient population.

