11.2. Study Population

The Intention-to-Treat (ITT) population: All participants who participate in the study and get randomized into one of the study's arm, without any major protocol violations which would significantly compromise the integrity of collected data.

The Modified Intent-To-Treat (Mod-ITT) Population: All participants from the ITT with a positive PCR or C&S results after randomization assignment.

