Appendix II. Urine Sample Collection

- Early morning urine specimens ('first void specimen') are preferred, however routine or random samples are acceptable.
- Upon sample collection, immediately refrigerate the specimen and submit to the central laboratory within 24 hours of collection (maintain at 2-8 °C when transporting).
- If transportation to the central laboratory is expected to exceed 24 hours, whole cups of urine specimen must be frozen. However, for expedited PCR test processing, aliquot 1mL of urine into two* separate 1.5mL Non-Stick RNase-Free microfuge tubes labeled with patient information. Aliquoted tubes (for PCR testing) and the remaining urine specimen in the cup (for C&S testing) must be place in the freezer (< -20°C).

UPH-STD-05-01 Version: 0

Effective Date: 06/23/2023 Page **39** of **44**

*One tube is for immediate processing on the following work day and the other is a backup in case testing needs to be repeated.

Methods	Supplies	Instruction
Clean-	- Sterile 90 mL container	Patient instructions:
catch	- Towelette	Step 1. Wash and dry your hands thoroughly.
Midstream		Step 2. Remove the container lid and set it aside. Do not touch inner surfaces.
		Step 3. Cleanse your urogenital area ("lower parts") with the towelette provided.
		Women: Wipe from front to back between the folds of skin.
		Continue to hold the skin fold apart until the urine sample is
		collected
		Men: Wipe the tip of the penis (if un-circumcised, retract the foreskin).
		Continue to hold the foreskin back until the urine sample is collected
		Step 4. Pass a small amount of urine into the toilet bowl.
		Step 5. Urinate into the container until the container is 1/2 to 2/3 full
		Step 6. Finish urinating into the toilet bowl.
		Step 7. Replace the lid and tighten firmly.
		Step 8. Wash and dry your hands thoroughly.

Note: The collector must NOT combine urine collected from separate voids to create one specimen of sufficient volume, under any circumstances.

Appendix III. Device specification: pathogen targets and Cq ranges, antibiotics resistance genes and Cq ranges

Pathogen targets	Cq ranges for pathogen detection
 Candida albicans, glabrata, parapsilosis, tropicalis 	
Chlamydia trachomatis	Critically High : 10.000 – 21.000
Citrobacter freundii/braakii	High : 22.000 – 26.000
Citrobacter koseri	Medium : 27.000 – 28.000
Enterococcus faecium, faecalis	Low : 29.000 – 32.000
Escherichia coli	Negative : 40.000 – 33.000;
Gardnerella vaginalis	09.000 - 1.000

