Klebsiella pneumoniae/oxytoca	
Mycoplasma genitalium	
Neisseria gonorrhoeae	
 Proteus mirabilis, vulgaris 	
Pseudomonas aeruginosa	
Serratia marcescens	
• Staphylococcus (coagulase negative: epidermidis,	
haemolyticus, lugdunensis, saprophyticus)	
Staphylococcus aureus	
Staphylococcus saprophyticus	

UPH-STD-05-01 Version: 0

Effective Date: 06/23/2023 Page **40** of **44**

Streptoccoccus agalactia (group B)	
Streptococcus pyogenes	
Trichomonas vaginalis	
Ureaplasma urealyticum	
Acinetobacter baumannii	
Antibiotic resistance genes	Cq ranges for resistance gene
• Class A β-lactamase; blaKPC	identification
• Class A β-lactamase; CTX-M-Group1	
 Class B metallo-β-lactamase; blaNDM 	Positive : 10.000 – 31.000
Class D oxacillinase OXA-48	Negative : 32.000 – 40.000;
Class D oxacillinase OXA51	1.000 - 9.000
• dfr (A1, A5), sul (1,2) probes (Sulfamethoxazole and	
trimethoprim)	
• ermB, C; mefA	
• IMP, NDM, VIM Groups (Carbapenem)	
MRSA* Mec-A	
• PER-1/VEB-1/GES-1 Groups (ESBL)	
• qnrA1, A2	
• qnrB	
• qnrS	
• tetB, tetM	
• VanA, VanB (Vancomycin)	
ACT, MIR, FOX, ACC Groups (Beta Lactams)	

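### The agreement analysis counts a PCR hit on any of 24 targets, five of them STI-causing by the protocol's own description, so STI-only, culture-negative patients lower NPA and overall agreement

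*Combined protocol and SAP*

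**What the plan says.** Section 3 reports that in validation the panel covered three classes: "15 bacterial genus and species, 4 fungal species, 5 STI-causing microorganisms, and 16 different classes of resistance genes". Section 9.1 drops the third class and describes "qualitative PCR amplification of target region of 24 uropathogens". Appendix III lists the targets in one column, with a single set of detection Cq ranges and no STI label. The list includes "Chlamydia trachomatis", "Mycoplasma genitalium" and "Neisseria gonorrhoeae", as well as Trichomonas vaginalis and Ureaplasma urealyticum.

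The culture method in section 9.1 uses a calibrated loop to "identify a quantitative count of bacteria at a lower limit of" 10⁵ CFU/mL. No organism list is given for it.

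Section 11.3.4 builds a 2×2 table of overall PCR result against overall C&S result, with PPA = a/(a+c) and NPA = d/(b+d). It offers these as estimates of the PCR's sensitivity and specificity. Positive and negative are not defined by organism. Section 11.3.1 uses ITT for this table and Mod-ITT for the primary and other secondary endpoints. Section 11.2 defines Mod-ITT as "All participants from the ITT with a positive PCR or C&S results after randomization assignment", again with no organism restriction. None of E1 to E8 addresses sexually transmitted infection, and no analysis rule deals with a result positive only for an STI target.

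**The concern.** The two tests in the agreement table do not have the same menu. The PCR reports five organisms that the protocol itself classes as STI-causing. The comparator is described only as a bacterial count with a threshold. A patient positive on PCR only for one of the five, with a negative culture, is counted as PCR-positive and C&S-negative. That is scored as disagreement whatever the PCR's accuracy for the other 19 targets.

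What is at stake is the reading of NPA. Part of any shortfall could come from what was on the panel rather than from false positives, and the single table planned cannot separate the two.

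The same gap touches the primary population. Neither the Mod-ITT definition nor the rule in 8.3 for a negative assigned test says whether an STI-only result counts, or that it counts in the same way in both arms. If Mod-ITT refers to either test, such patients enter from both arms. If it refers to the assigned test, they enter from the PCR arm only.

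**Working it through.** **1. The count of 24.** Section 3 gives 15 + 4 + 5 = 24, which matches section 9.1. Appendix III has 21 rows. Counting the Candida row as four species gives 21 − 1 + 4 = 24. Taking out the four Candida species and C. trachomatis, M. genitalium, N. gonorrhoeae, T. vaginalis and U. urealyticum leaves 24 − 4 − 5 = 15 bacterial targets, which agrees with section 3. So 5 of 24 targets (20.8%) are STI-causing by the protocol's description, and 19 are bacterial or fungal. Appendix III does not label the five, so naming them is an inference that fits the count.

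**2. Direction of the effect on the table.** Compare the all-target rule with a rule that counts only the 19 targets.

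- STI-only on PCR, culture negative: in cell b under the all-target rule, in cell d under the 19-target rule. The all-target rule lowers NPA = d/(b+d) and overall agreement. PPA = a/(a+c) does not move.
- STI-only on PCR, culture positive for an organism PCR missed: in cell a under the all-target rule, in cell c under the 19-target rule. The all-target rule raises PPA and overall agreement.

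**3. Size.** Let s be the share of all patients who are STI-only and culture-negative, and B the culture-negative share. Then the fall in NPA is s/B and the fall in overall agreement is s. The documents give neither s nor B, so what follows is illustration. Assume 720 patients, B = 50% (360 patients), PPA 90% and a 19-target NPA of 80%. Then a = 0.90 × 360 = 324, d = 0.80 × 360 = 288, and overall agreement is (324 + 288)/720 = 85%. All both-negative patients are assumed to stay in the table.

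| s | patients | NPA, all targets | fall in NPA | overall agreement | PPA |
|---|---|---|---|---|---|
| 1% | 7.2 | 280.8/360 = 78% | 2 points | 604.8/720 = 84% | 90% |
| 3% | 21.6 | 266.4/360 = 74% | 6 points | 590.4/720 = 82% | 90% |
| 5% | 36 | 252/360 = 70% | 10 points | 576/720 = 80% | 90% |

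The fall in NPA depends on B but not on the starting NPA. With B = 60% it is 1.7, 5.0 and 8.3 points; with B = 40% it is 2.5, 7.5 and 12.5 points.

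**4. The primary endpoint.** An exact enumeration of the one-tailed Fisher test at 0.70 versus 0.80 with 287 per arm gives power 0.8513, as printed in section 11.1. Now let STI-only patients make up 5% or 10% of each arm, an assumed share.

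- If they respond at 70% in both arms, power falls to 81.4% or 77.2%.
- If they respond at 50% under C&S and 80% under PCR, power rises to 90.4% or 94.1%.

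The direction depends on response rates that the documents do not give.

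**The case against.** The strongest reply is that the protocol means to include these patients. Section 3 counts urethritis as a lower tract infection and says a wider range of organisms may cause UTI. Section 9.1 calls all 24 targets uropathogens, and the sample report in Appendix IV lists STI targets under a urinary-tract heading. Every patient must also meet I2 to I5, including the investigator's suspicion of cUTI. This stands. A reader might infer that STI-only patients are wrongly analysed as cUTI and should leave the primary population, but the documents do not support that. It is a choice of case definition, and the protocol's text leans towards inclusion.

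A reader might also infer that agreement as a whole is lowered. It is not: PPA is unaffected or raised.

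Three further points stand in part. First, that any detection counts as positive is the natural reading of 11.3.4 and of the sample negative report, not a written rule. Second, section 9.1 lists no organisms for culture, so the claim that culture does not look for the five is an inference; the arithmetic needs only that the patient is culture-negative. Third, a method described as a bacterial count may not report fungi either. The four fungal targets are kept among the 19 because section 3 names yeast among the causes of UTI and does not class fungi as STI-causing. An organism-level listing would show whether they also drive disagreement.

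Finally, agreement is a secondary, descriptive result. That limits the weight of the point but does not remove it, because the plan invites readers to take NPA as specificity.

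**Conclusion.** The point holds for the agreement analysis. On the natural reading of 11.3.4, STI-only, culture-negative patients lower NPA by s/B and overall agreement by s. At 50% culture-negative, that is 2, 6 or 10 points of NPA for an assumed 1%, 3% or 5%. The true rate is not in the documents and could be near zero. The result also assumes that both-negative patients remain in the table, although 8.3 removes them from the study.

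For the primary endpoint, the documents show a missing rule but no bias of known direction. A reader might infer that the primary comparison is distorted in favour of one arm. That does not follow: under the either-test reading such patients enter from both randomised arms, and power can move either way. Under the assigned-test reading they would enter from the PCR arm only and the arms would not be comparable. The text does not settle which reading applies, which is why one written rule is needed. This is an inexpensive improvement to the analysis definitions.

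**What to change.** - **Section 11.3.4.** Compute PPA and NPA with PCR-positive defined as detection of at least one of the 19 bacterial or fungal targets. Report the all-target version alongside. Name the five STI targets in Appendix III, and list STI-only patients separately by arm with their culture result.
- **Section 11.2.** Keep the primary Mod-ITT. State one rule for STI-only results that applies identically in both arms; section 5.1 has every sample tested by both methods, so the classification is available for all patients. Add a sensitivity analysis of the primary endpoint without STI-only patients.
- **Wording to reconcile.** Sections 7.5, 8.3 and 11.2 each refer to a negative or positive test in different, undefined terms. They should be brought into line. No change to the 8.3 pathway is asked for: redefining a negative result there would alter who is referred to SOC and who is excluded, which goes beyond an analysis change.

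The cost is some protocol wording, one derived variable, a second agreement table and one sensitivity analysis. No new data are needed.

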9.2. Body Temperature

Body temperature will be measured at Visit 1, Visit 3, and possibly at unscheduled visits. Temperature should be measured orally, rectally, or by tympanic route. Temperature should be assessed as per institution guidelines while at the study site, and recorded in the eCRF.

9.3. Blood Pressure and Heart Rate

Blood Pressure and Heart Rate will be measured at Visit 1, Visit 3, and possibly at unscheduled visits. Blood Pressure and Heart Rate will be measured according to the site's SOPs. Additional Blood Pressure and Heart Rate collections or changes to collection times will be permitted, as necessary, at the discretion of the Investigator to ensure proper collection of safety data. Appropriately sized and calibrated equipment will be used at each measurement of Blood Pressure and Heart Rate.

9.4. Physical Examination

The Investigator or delegate will perform a physical examination at V1 and V3. The physical examination may be complete, targeted, or omitted at the Investigator's discretion, based on the patient's condition and circumstances.

9.5. Termination of the Study

The study may be terminated at any time by the Sponsor, PI, or applicable regulatory authority (IRB). If the study is terminated prematurely, the PI/Investigator(s), patients, and the regulatory authorities must all be notified of the termination promptly. Upon termination of the study whether premature, or due to completion, site close-out activities will be initiated including regulatory close-out to the appropriate authorities.

10. SAFETY INSTRUCTIONS AND GUIDANCE

UPH-STD-05-01 Version: 0

Effective Date: 06/23/2023 Page **24** of **44**

10.1. Definitions of Adverse Events (AEs)

10.1.1. Adverse Event

Definition: An adverse event can be any unfavorable and unintended sign, symptom, or disease that happens during the study participation (defined as after the time of initial informed consent), whether or not it is considered study drug, device, or procedure-related. Adverse event (AE) may be mild, moderate, or severe, and may be caused by something other than the drug or therapy being given. A pre-existing condition is one that is present at study entry and is reported as part of the subject's medical history; if the frequency, intensity, or character of the condition worsens during the study participation, it should be reported as an AE. Any abnormality that presents during a medical test is to be defined as an AE if it produces clinical signs and/or symptoms, requires intervention, or deemed clinically significant by the investigator. Subject should be instructed to report all AEs to the investigators or study staff. Adverse events must be followed-up to resolution or when the condition is deemed stable by the Investigator.

10.1.2. Serious Adverse Event

A Serious Adverse Event (SAE) is any AE, regardless of causality that results in any of the following:

- Death;
- Life-threatening AE;
- Requires inpatient hospitalization;
- Persistent or significant disability/incapacity or;
- Medical event that may jeopardize the patient/subject and may require medical or surgical intervention.

10.2. Collecting, Recording, and Reporting of AEs

10.2.1. Collecting and Recording

The Investigator or delegated study staff must record all adverse events in an AE form with information about:

- Details of adverse event
- Date of onset (time can be recorded, if applicable)
- Intensity (mild, moderate, severe)
- Causal relationship to study involvement (probable, possible, unlikely, not related)
- Other actions taken
- Date and time of outcome

UPH-STD-05-01 Version: 0

Effective Date: 06/23/2023 Page **25** of **44**

Document Ref: WQAPR-C9AUZ-GYNVC-SHXJH

Outcome

All AEs, regardless of causal relationship to study involvement, spanning from the signature of the informed consent form until the end of the study as defined by the protocol for that subject, are to be recorded on the corresponding eCRF.

10.2.2. Guidelines for Reporting Adverse Events

The following timelines apply to the reporting of AEs/SAEs as applicable. The Investigator must notify the Sponsor:

- Within 24 hours of the Investigator becoming aware of the event if it results in death of a patient
- Within 2 weeks (10 business days) after becoming aware of the event if:
 - o It is an AE which is related to the conduct of the study;
 - o It is an AE that is expected (listed in the ICF as a potential side effect) but is occurring more frequently than expected;
 - It is an unexpected AE/SAE that is related to the conduct of the study but is not life-threatening
- Annually or upon study completion (together with the Study Status Report) if:
 - o It is an expected AE (listed in the ICF as a potential side effect);
 - It is an unexpected AE that is unlikely to be related to the conduct of the study and is not life-threatening.

During the course of a clinical study, the sponsor shall notify the IRB of any suspected adverse reaction to study treatment that is both serious and unexpected:

- A single occurrence of a serious, unexpected event that is uncommon and strongly associated with drug exposure;
- A single occurrence, or more often a small number of occurrences, of a serious, unexpected event that is not commonly associated with drug exposure, but uncommon in the study population;
- Multiple occurrences of an AE that, based on an aggregate analysis, is determined to be an unanticipated problem;
- An AE that is described or addressed in the investigator's brochure, protocol, or informed consent documents, but occurs at a specificity or severity that is inconsistent with prior observations;
- A serious AE that is described or addressed in the investigator's brochure, protocol, or informed consent documents, but for which the rate of occurrence in the study represents a clinically significant increase in the expected rate of occurrence;
- Any other AE or safety finding that would cause the sponsor to modify the investigator's brochure, study protocol, or informed consent documents, or would prompt other action by the IRB to ensure the protection of human subjects.

UPH-STD-05-01 Version: 0

Effective Date: 06/23/2023 Page **26** of **44**

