14.4. Risks and Procedures to Minimize Risk

Potential risks are disclosed to the study patients in the ICF prior to their participation in the study. The risk of the therapeutic intervention is judged comparable in comparison to standard of medical care. The proposed investigations and management strategies are all part of routine optimal care. The identifiable risks are associated with cUTIs. These risks include but are not limited to:

- Allergic reaction to antimicrobial therapy
- Progression or relapse of cUTI
- Nausea, vomiting, headache, skin rash, hypersensitivity reaction, anaphylaxis reaction
- Yeast infection (vaginitis/vulvovaginal candidiasis)
- Progression to acute renal failure

UPH-STD-05-01 Version: 0

Effective Date: 06/23/2023 Page **32** of **44**

- C. difficile infection
- Sepsis

There may be unknown risks.

While there is minimal potential risk of loss of privacy and loss of confidentiality, multiple precautions will be in place to protect the subject's privacy.

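### Section 10.2.2 takes non-fatal life-threatening events out of two slower reporting items but gives them no faster tier, so they are due in 10 business days, yearly, or by no stated deadline

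*Combined protocol and SAP*

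**What the plan says.** Section 10.2.2 sets three tiers for notifying the sponsor and applies them to AEs and SAEs alike.

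- **24 hours.** One trigger: "Within 24 hours of the Investigator becoming aware of the event if it results in death of a patient".
- **10 business days.** The tier opens "Within 2 weeks (10 business days) after becoming aware of the event if" and has three items. The first is general: "It is an AE which is related to the conduct of the study". The second covers an expected AE, "but is occurring more frequently than expected". The third is specific: "It is an unexpected AE/SAE that is related to the conduct of the study but is not life-threatening".
- **Yearly or at study end.** Two items. The first is general: "It is an expected AE (listed in the ICF as a potential side effect". The second covers unexpected AEs that are unlikely to be related and are not life-threatening.

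Section 10.1.2 lists "Life-threatening AE" as a criterion for seriousness, separate from death, and gives no reporting time. Section 14.4 says that potential risks are disclosed in the consent form. Its list includes anaphylaxis, sepsis and "Progression to acute renal failure". Section 10.2.1 requires every AE, whatever its cause, to be recorded on the eCRF. Section 10.4 promises prompt handling, compliance with the applicable rules and inclusion in the final report. Neither section gives a number of hours or days.

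**The concern.** Limiting an item to events that are not life-threatening makes sense only if life-threatening events are dealt with somewhere faster. Here the only faster tier is for deaths, so the exclusion leads nowhere. A site that follows the tiers exactly would send a non-fatal life-threatening event on a slow timetable, or would find no timetable for it.

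What is at stake is how soon the sponsor learns of such an event. The trial enrolls elderly, pregnant and immunosuppressed patients and patients with chronic kidney disease (section 6.1). Treatment is to start within 24 hours of the assigned test result (Table 1, note f), and section 3 puts culture at 48 hours or more against typically under 24 hours for PCR. A difference between arms in serious progression of infection is therefore plausible. No interim analysis is planned (section 5.4), and the available text describes no data monitoring committee, so individual reports are the main early warning. A patient is in the study for about 28 days (section 5.3.1), so a yearly report can arrive long after that patient has left.

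**Working it through.** No sample size, power or error rate is involved. The check is to apply the six conditions in section 10.2.2 literally to every kind of non-fatal life-threatening event.

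Conventions:

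- An SAE is a kind of AE (section 10.1.2), so items written for AEs also cover SAEs.
- Section 10.2.1 grades causality on four levels. I count the upper two as related and the lower two as unrelated.
- Expected means listed in the consent form. The more-frequent condition can apply only to expected events.

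This leaves 2 × 3 = 6 combinations:

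| Related? | Expected? | More frequent than expected? | Tier(s) reached |
|---|---|---|---|
| Yes | Yes | Yes | 10 business days and yearly |
| Yes | Yes | No | 10 business days and yearly |
| Yes | No | n/a | 10 business days, through the general related-AE item only |
| No | Yes | Yes | 10 business days and yearly |
| No | Yes | No | Yearly only |
| No | No | n/a | None |

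Three results follow.

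1. None of the six reaches the 24-hour tier. Every fatal combination does.
2. Three of the six fall in two tiers at once, and section 10.2.2 does not say which prevails.
3. One of the six, unexpected and unrelated, falls in no tier. The one item that would otherwise hold it, the second yearly item, excludes life-threatening events.

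The third row shows the gap most clearly. The item written for unexpected related events excludes life-threatening ones, and the general related-AE item then brings them back at the same 10-business-day limit. The exclusion changes nothing.

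Size of the delay: the protocol equates 10 business days with 2 weeks, and 14 days × 24 hours = 336 hours. Against 24 hours for a death, that is 336 / 24 = 14 times as long. The yearly tier can reach 12 months.

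For comparison, I applied the same conditions to events that are neither fatal nor life-threatening, which include SAEs through hospitalization or disability. All six combinations reach at least one tier and none reaches 24 hours. The same three combinations fall in two tiers.

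**The case against.** The strongest reply is that other provisions keep these events in view. All AEs go on the eCRF (10.2.1), monitoring is risk-based (15.2), CRF data are checked against source (15.2.3), and 10.4 commits to prompt and compliant reporting. This defeats one tempting reading, that such events might never reach the sponsor. The documents do not support it, because the events are recorded and go into the final report. What these sections lack is a deadline, so they do not repair the tiers.

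Three other readings also go too far.

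- **That any event named in the consent form waits a year.** The yearly tier stands alone only when the event is expected, unrelated and not more frequent than expected. The 10-business-day tier applies if it is related or more frequent. The consent form is not available, and section 14.4 describes its list as risks associated with cUTI, so the form may not present sepsis or renal failure as side effects. Hospitalization as such is not on that list. The more-frequent item is a real safeguard, though a limited one, since an investigator at one of at least six sites may not see an excess that appears only across sites.
- **That the sponsor's onward duties are breached.** Section 10.3 concerns SAEs considered related to the device, and the IRB duty in 10.2.2 is introduced for suspected reactions to study treatment. Events classed as related to the study still arrive within 10 business days, and no sponsor-to-IRB deadline is stated that this would break.
- **That every SAE must move to 24 hours.** Section 10.2.2 names SAEs when it places unexpected, related, non-life-threatening events at 10 business days. That looks deliberate, and nothing in the documents shows it to be a mistake.

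**Conclusion.** The concern holds as a gap in section 10.2.2. Only death triggers 24-hour notification. A non-fatal life-threatening event is due in 10 business days, in 10 business days and yearly at once, yearly only, or by no stated deadline, depending on relatedness, expectedness and frequency. The tier structure follows from the text alone. The examples of sepsis, anaphylaxis and acute renal failure in the yearly tier rest on the assumption that the consent form lists the section 14.4 risks as potential side effects.

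The point bears on safety oversight. It does not touch the primary endpoint, the type I error, the power or the sample size. It should be corrected, because a site that complies fully would still be slow to pass on information about life-threatening events.

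**What to change.** Reconcile sections 10.1.2, 10.2.2, 10.3 and 10.4:

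1. Add non-fatal life-threatening events to the 24-hour investigator-to-sponsor tier, whatever their relatedness or expectedness.
2. Exclude them from the general related-AE item and the general expected-AE item.
3. State that the faster tier prevails whenever an event meets more than one item.
4. Have the sponsor confirm which single tier applies to each other kind of SAE, such as hospitalization or disability.

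The cost is new wording in section 10.2.2, site training and a few more expedited forms.
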